Secondary research questions: What is the effect of the mentorship intervention on the following **short-term and intermediate outcomes**: social support at work, job satisfaction, and intention to leave construction trades? Hypothesis: expect an improvement (increase) in these outcomes among the intervention group compared to controls

Other (process and longer-term health) outcomes we will consider in a second paper where we'll conduct a more exploratory analysis by group:

- Self-reported health
- Self-reported mental health
- Sleep quality
- Sought professional help for mental health
- Sickness presenteeism
- Physical activity outside work
- Insomnia
- Depression severity
- Anxiety severity
- Work/life conflict
- Demand/control
- Overcompensation
- Bullying
- Age discrimination
- Race discrimination

- Gender discrimination
- Tokenism
- Sexual harassment
- Injury at work
- Work injury severity
- frequency of being understood
- perceived effectiveness at communicating
- self-advocacy behaviors
 - formal skills training
 - goal setting
 - perceived progress towards goals
 - perceived ability to advocate for own needs on jobsite

Data

Two control (total n = 40) and intervention (total n = 56) cohorts surveyed at three timepoints each: baseline, 6 months, and 1 year.

Subset of 18 control and 16 mentees who completed surveys at all three timepoints.

Variables to be used in descriptive analysis

Demographics by group:

- Age
- Race/ethnicity

- Marital status
- Family annual income
- Education
- Years in construction industry

Baseline variables by group:

- Mentor experience
- Mentor type
- Formal mentorship training
- Local level mentorship

Variables to be used in primary analysis

Exposure: group – 0 for control, 1 for intervention

Outcome: perceived stress score (continuous)

Fixed effects: time, group x time

Random effect: union local

Covariates: age, race/ethnicity, family annual income, year in apprenticeship, size of local,

region of the country

Variables to be used in secondary analyses

Exposure: group – 0 for control, 1 for intervention

Secondary outcomes: Social support at work (continuous), Job satisfaction (continuous),

Intention to leave construction trades (categorical)

Fixed effects: time, group x time

Random effect: union local

Covariates: age, race/ethnicity, family annual income, year in apprenticeship, size of local,

region of the country

Statistical methods

Software: R

Analysis of loss to follow-up

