Compare those who dropped out to those who stayed in study by:

- Union local [tally]
- Race/ethnicity
- Age
- Marital status
- Dependents
- Stress at baseline
- Years in construction industry
- Intervention status [yes/no]

- Round
- Intention to leave construction industry
- Difficulty taking time off during work to take care of personal or family matters
- Frequency of interference between job demands and family life or personal time
- Frequency of interference between family demands and work

And/or model for loss of follow up to include group, round, plus other vars listed above

Use chi-square test of independence (for discrete variables)/Fisher's Exact test (for count data, small sample sizes)/t-test (for continuous variables)/Wilcoxon rank sum test (for continuous variables not normally distributed)

Bivariate analysis

With same tests as above, compare demographic and other sample characteristics by arm at baseline

With same tests as above, compare primary and secondary outcomes by arm at baseline, midyear, and end-year; also do by round

With same tests as above, do same comparison for subset of respondents in each arm who have surveys at all three timepoints; also do by round

Graph observations (averages, error bars). Spaghetti plots showing trajectories for each person, by group. Stratify by group, explore change btw timepoints. Either paired t-test or single rank Wilcoxon test. First compare BL to MY, then MY to EY.

Multivariate analysis

From research strategy: To evaluate changes over time, effectiveness of the intervention will be analyzed using a mixed effects regression model. For our primary outcome (perceived stress scale, PSS), a base model will be developed with PSS as a function of arm (intervention/control), and survey (pre, 6 months, post), with a random effect for local union (to assess difference between locals, and to control for non-independence within locals). We will then test the contributions of additional co-variates, including demographics, year in apprenticeship, size of local, and region of the country, etc. Co-variates will be retained if they are statistically significant (p<0.1) or change the coefficient for study arm by \geq 10%. Similar models will subsequently be run for each short-term and intermediate outcome.

Table shells -> see SMART Training Program_Survey responses + table shells_17Jun24.xlsx

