Table 1: Baseline characteristics of participants (n=X), by study arm [+ outcomes at baseline for descriptives, may not use]

Table 2: Effect of mentorship training on level of perceived stress among tradeswomen using mixed effects regression models; base model + models with added covariates, in stages

Table 3: Effect of mentorship training on [X secondary outcomes] among tradeswomen using mixed effects regression models; base model + models with added covariates, in stages

Notes

Keep track of remaining tasks and questions here. Update with steps taken and info obtained as tasks are completed.

Survey data

Estimated missingness for each variable.

Filled in sources as best as I could in scale source doc.

Data dictionary – For scores that we modified, proposed strategy (mostly should just be average score, but noted any alternatives reported in the literature, e.g. if others that are unaltered but just subset of questions and whether others have done that, whether they standardized the scale to the original i.e. by multiplying total by old max divided by new max).

SMART Women_Variable info – summarizes variables we plan to analyze, their type (demographic/confounder, outcome, mediator) and how they'll be categorized.

Working list of analytic steps to do in R

Conduct descriptive analysis of demographic characteristics by study arm (intervention/control) using relevant statistical test. Also check balance in terms of year in apprenticeship, size of local, and region of the country.

Analysis of loss to follow-up:

- Union local size [tally cioè of n ppl in local?]
- Race/ethnicity
- Age
- Marital status
- Dependents [y/n]
- Stress at baseline
- Years in construction industry
- Intervention status [group]
- Round
- Intention to leave construction industry
- Difficulty taking time off during work to take care of personal or family matters
- Frequency of interference between job demands and family life or personal time
- Frequency of interference between family demands and work

Visualize outcomes by group at each time point --> did this implicitly by running tests automatically in crosstables. If outcomes not normally distributed, compare groups at each timepoint (not differences) using Wilcoxon ranksum test (rather than two sample t-test). Complete responses. Will tell us if have group diffs at each timepoint.

once have dates, edit code and add to plots by round (all data, complete responses)

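### No outcome model adjusts for a woman's baseline score or links her surveys, so the arm contrast is less precise than the data allow

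*Combined protocol and SAP*

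**What the plan says.** The Analysis plan, under *Variables to be used in primary analysis*, gives "Fixed effects: time, group x time" and "Random effect: union local", with "Covariates: age, race/ethnicity, family annual income, year in apprenticeship, size of local" and region of the country as covariates. The secondary analyses repeat this list. The baseline score of the outcome is not in it.

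*Multivariate analysis* describes the base model as "PSS as a function of arm (intervention/control), and survey (pre, 6 months, post), with a random effect for local union". It has no interaction, and baseline is one of the three response occasions. Further covariates, "including demographics, year in apprenticeship, size of local, and region of the country, etc", are kept only if they reach p<0.1 or move the arm coefficient by at least 10%. The end of *Working list of analytic steps to do in R* restates this model.

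*Bivariate analysis* compares the outcomes by arm separately at baseline, midyear and end-year. For non-normal outcomes the working list says to "compare groups at each timepoint (not differences) using Wilcoxon ranksum test". The Table 1 shell leaves it open whether baseline outcomes will be shown.

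**The concern.** A woman's baseline score is usually the best single predictor of her later score. Here it does no predictive work in any outcome model: it is a response row, and with no participant term the model treats her three surveys as unrelated apart from sharing a local.

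Precision is scarce. About 100 women per arm were planned. *Data* reports 40 control and 56 intervention women, of whom 18 and 16 completed all three surveys. A raw follow-up comparison also carries forward a share rho of any chance baseline difference between arms: a difference of 0.2 SD would move it by 0.2 x 0.5 = 0.1 SD at rho = 0.5.

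The treatment contrast is also unsettled. The variable list implies group by time, whereas the base model offers only an arm coefficient averaged over all surveys, including the one taken before any mentoring.

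**Working it through.** **Inputs.** From *Data*: 40 and 56 women; 18 and 16 with all three surveys. From *Recruitment and Assignment of Locals*: 26 locals with five or more women apprentices. The plan states no alpha, power, effect size, SD, intracluster correlation (ICC) or between-survey correlation, so it has no figure to reproduce. Assumed: equal correlation rho between any two surveys, 0.3 to 0.7; equal variance at each survey; two-sided 0.05 and 80% power; 13 locals per arm; ICC 0 or 0.05.

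**Variance of the arm contrast at one follow-up**, in units of sigma²(1/n1 + 1/n2), complete data, no clustering: raw follow-up = 1; group by time (difference in change) = 2(1 − rho); baseline-adjusted = 1 − rho².

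| rho | Raw | Group by time | Adjusted | Saved v. raw | Saved v. group by time |
|---|---|---|---|---|---|
| 0.3 | 1 | 1.40 | 0.91 | 9% | 35% |
| 0.5 | 1 | 1.00 | 0.75 | 25% | 25% |
| 0.7 | 1 | 0.60 | 0.51 | 49% | 15% |

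At rho = 0.5 the SE falls by 1 − √0.75 = 13%.

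**In SD units at rho = 0.5.** With 40/56, √(1/40 + 1/56) = 0.207, and adjusted 0.207 x √0.75 = 0.179. Multiplying by 1.960 + 0.842 = 2.802, the detectable difference goes from 0.58 to 0.50 SD. With 18/16, √(1/18 + 1/16) = 0.344, adjusted 0.298, and the detectable difference goes from 0.96 to 0.83 SD.

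**Effect of the missing participant term.** With a local effect only and ICC 0, the model treats a woman's surveys as independent, so it reports an SE of √2 x 0.207 = 0.293 for the 1-year interaction whatever rho is. The true SE is 0.245, 0.207 and 0.160 at rho 0.3, 0.5 and 0.7. At ICC 0.05 and rho = 0.5, a generalised-least-squares calculation gives 0.285 reported, 0.207 true and 0.183 for the adjusted contrast.

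**With heavy loss.** Suppose all 96 women have a baseline score and only 18/16 have follow-ups (ICC 0, rho = 0.5). The planned interaction then has true SE 0.344 (reported 0.401), a participant effect alone brings it to 0.315, and baseline adjustment gives 0.298. Once a participant effect is in place, the further variance saving is 1 − (0.298/0.315)² = about 10%.

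**Arm-plus-survey base model.** With complete data the arm coefficient averages three surveys. A constant follow-up effect d gives (0 + d + d)/3 = 0.67d. Its true SE is 0.207 x √((1 + 2rho)/3) = 0.169 at rho = 0.5, against 0.120 reported by the local-only model. Rescaled to d, 0.169/0.67 = 0.25, against 0.179 for the adjusted contrast. Under the heavy-loss pattern, weighting each survey by n1n2/(n1 + n2) gives 23.3 at baseline and 8.47 at each follow-up, so the coefficient recovers 16.94/40.27 = 0.42d.

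**The case against.** The best defence is that baseline is already in the model. As a response occasion with a group-by-time term, it yields a difference in change, and adding it as a covariate to that model would put it on both sides. Baseline as response is a legitimate choice, but it matches the precision of adjustment only if the arms share a baseline mean and a woman's surveys are linked. The plan provides neither. The open-ended covariate list does not help: anything added faces the significance or 10% screen, and baseline cannot sensibly be added while it remains a response row.

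A reader might infer that baseline stress is used nowhere. That is not so: "Stress at baseline" is among the variables for the optional loss-to-follow-up model. A reader might also take the working-list remark "compare groups at each timepoint (not differences) using Wilcoxon ranksum test" to describe every arm test. It belongs to one bivariate step, conditional on non-normality. The group-by-time contrast is a difference, and paired tests of change are planned within each arm, although these give no comparison between arms. Nor do the documents show a baseline score for every woman; the notes mention missingness for each variable.

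It is true that the arm-plus-survey coefficient has a smaller SE (0.169) than the adjusted contrast (0.179). It estimates a diluted quantity, however, and the advantage reverses once that is allowed for.

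The objection with most force concerns exchangeability. Locals were assigned first and women recruited afterwards, into a mentoring programme in one arm and into questionnaires only in the other. Baseline differences may therefore reflect selection, and baseline adjustment is then not automatically better than a change contrast. This stands and shapes the fix.

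**Conclusion.** The point holds for the outcome models and the bivariate arm comparisons: none adjusts for the baseline score of the outcome, and the models do not link a woman's surveys. Over rho 0.3 to 0.7, adjustment saves 35% to 15% of the variance against group by time with complete data, and 9% to 49% against raw follow-up comparisons. It is tempting to call this a loss of a quarter of the trial's precision. The documents do not support a single figure: 25% is variance, not SE, and holds only at an assumed rho of 0.5. The ranges assume equal variances and correlations and, for the closed forms, no clustering.

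The group-by-time contrast is not biased by omitting the covariate. Under the complete-data assumptions above, its local-only SE is too large. If the arm coefficient of the base model is read as the effect, the fault is dilution, to about 0.67 of a constant follow-up effect with complete data.

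**What to change.** For perceived stress, social support and job satisfaction:

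- Model the 6-month and 1-year scores with arm, time, arm by time, the baseline score of the same outcome, and baseline by time. Always include the baseline terms, exempt from the p<0.1 or 10% screen.
- Use random effects for local and for participant within local.
- Name the adjusted arm difference at a stated follow-up as the treatment contrast, and use the same wording in the variable lists, *Multivariate analysis* and the working list.
- Report baseline-adjusted arm differences beside the bivariate tests, and always show baseline outcomes by arm in Table 1.
- Keep the group-by-time contrast, with a participant effect, as a sensitivity analysis against selection at recruitment.

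The cost is one or two degrees of freedom. Women without a baseline score, or without any follow-up score, do not contribute to the adjusted contrast, and the plan should say so. The working list indicates that some bivariate tests have already been run, so the change must be logged as a dated amendment.

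### The loss-to-follow-up analysis uses one dropped-out/stayed split and baseline stress only, so it cannot show whether loss after the 6-month survey follows 6-month stress

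*Combined protocol and SAP*

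**What the plan says.** The *Data* section of the Analysis plan describes "Two control (total n = 40) and intervention (total n = 56) cohorts surveyed at three timepoints each: baseline, 6 months, and 1 year". It then gives the complete cases: "Subset of 18 control and 16 mentees who completed surveys at all three timepoints".

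Under *Analysis of loss to follow-up* the instruction is "Compare those who dropped out to those who stayed in study by", followed by a list of variables. The only stress item is "Stress at baseline". The *Working list of analytic steps to do in R* repeats that item and adds no later score. Intention to leave and the work-family items are listed without a timepoint.

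A regression is offered as an option: "And/or model for loss of follow up to include group, round, plus other vars listed above". It takes its variables from the same list, so it adds neither 6-month stress nor the interval in which a woman was lost. Round reads as the recruitment cohort, because *Bivariate analysis* asks for the comparisons at each survey to be repeated by round.

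For a continuous variable such as stress, the test is a "t-test (for continuous variables)/Wilcoxon rank sum test (for continuous variables not normally distributed"). The plan does not define dropping out and gives no significance level for these tests.

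**The concern.** Perceived stress is the primary outcome, and mentoring is meant to change it after baseline. For a woman who answers at 6 months and misses the 1-year survey, the 6-month score is the measurement closest to her loss and may already reflect the intervention. The loss analysis does not use it. A single split also lets early and late loss fall into one group, and possibly a missed middle survey too, which weakens any signal confined to one interval.

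Selective late loss could matter for the main result. The primary analysis lists "Random effect: union local" and no participant-level term. As listed, the model does not use a woman's own 6-month score to inform her missing 1-year score. If late leavers are the more stressed women, mean 1-year stress among those still observed in an affected arm will be too low.

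**Working it through.** **Inputs from the documents.** Enrolled: 40 + 56 = 96. All three surveys: 18 + 16 = 34, or 34/96 = 35.4%. At least one survey missing: 96 − 34 = 62, or 62/96 = 64.6%. By arm, 22/40 = 55.0% of controls and 40/56 = 71.4% of the intervention group are incomplete. The plan states no power for the loss analysis, so there is no figure of its own to reproduce.

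**Is the question answered elsewhere in the plan?** *Bivariate analysis* compares stress by arm at each survey, for all respondents and for women with all three surveys. It also compares change between surveys within each group and plots individual trajectories. Read side by side, these give an informal view. None of them tests 6-month stress between women lost afterwards and women who stayed.

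**Assumptions (not in the documents).** Two-sided alpha 0.05. Stress normally distributed. Loss at 6 months random. Loss at 1 year logistic in 6-month stress, with an odds ratio of 2 per SD. Correlation between surveys 0.5 to 0.7. The documents do not give the timing of loss, so four pairs of response probabilities (6 months, 1 year) were used, each matching 34/96 = 0.354:

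- 0.5 × 0.7 = 0.35
- 0.6 × 0.6 = 0.36
- 0.7 × 0.5 = 0.35
- 0.8 × 0.44 = 0.352

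**Checks compared by simulation, 96 women per data set.**

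| Check | Power over all scenarios | Middle case (0.6, 0.6; correlation 0.6) |
|---|---|---|
| Planned: t-test of baseline stress, completers v all others | 10–42% | 20% |
| Baseline stress, comparison limited to loss after 6 months | 17–49% | – |
| Direct: t-test of 6-month stress among 6-month responders | 53–81% | 68% |

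The second row shows that splitting by interval is not enough. Most of the gain comes from using the 6-month score.

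**Wider grid.** 20, 31 or 42 of the 62 lost before 6 months; correlation 0.3, 0.5 or 0.7:

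| Odds ratio per SD | Planned check | Direct 6-month check |
|---|---|---|
| 1.5 | 5–18% | 28–39% |
| 2 | 7–41% | 60–81% |
| 3 | 10–70% | 92–99% |

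The planned check is below 50% in 25 of these 27 scenarios. With no true dependence, both checks reject at 5%.

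**Size of the possible bias.** With 31 lost in each interval, correlation 0.5 and odds ratio 2, mean 1-year stress among those still observed is about 0.15 SD too low in an affected arm. Over the grid the range is roughly 0.05 to 0.30 SD. If both arms are affected equally, the shift largely cancels in the comparison between them.

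**Dependence that differs by arm** (31 lost in each interval, correlation 0.5, odds ratio 2). If it is confined to the intervention arm, the planned check finds it in 10% of data sets and the pooled 6-month check in 32%. If it runs in opposite directions in the two arms, both pooled checks stay near 6–7%, while a group × 6-month-stress term finds it in about 68%.

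**The case against.** The strongest objection is that the low power depends on early loss being unrelated to stress, for which the documents give no basis. This stands. If early loss also has an odds ratio of 2 per SD of baseline stress, the planned comparison flags stress-related loss in about 55 to 91% of simulated trials. The planned check also does better when nearly all loss is late and dependence and correlation are strong: up to 94% with no early loss, odds ratio 3 and correlation 0.8. In none of these cases can it show whether late loss follows 6-month stress.

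Second, dropping out is undefined, so completers against everyone else is one possible coding. This also stands, and it is a reason to define loss by interval.

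Third, a reader might infer that this check is the plan's only evidence on stress and loss, or that the stress model will be trusted because of it. The documents support neither. The midyear tables and trajectory plots give informal evidence, and no conclusion in the plan is made to depend on the loss analysis.

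Fourth, an obvious remedy is to stack both follow-up surveys and fit one coefficient for the last observed stress score. That does not deliver the gain. Its simulated power is about 10 to 62%. In the middle case it is 16 to 46%, depending on what is assumed about 1-year response among women who missed 6 months. If loss is monotone it is little or no better than the planned check, because the single coefficient averages the informative rows with rows that carry no late-loss signal.

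**Conclusion.** The concern holds in a limited form. As written, the loss analysis cannot show whether loss after 6 months follows 6-month stress. If early loss is unrelated to stress and late loss has an odds ratio of 2 per SD of 6-month stress (correlation 0.5 to 0.7), it would detect the dependence in about 10 to 40% of trials, against about 50 to 80% for a direct comparison. If early loss also depends on stress, it will often flag a problem without dating it.

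Two stronger readings are not supported. One is that the planned check would generally miss stress-related loss. The other is that loss in this trial is in fact driven by stress. The documents give no correlation, no timing of loss and no stress data by follow-up status. The point is an inexpensive improvement to the attrition analysis of the primary outcome, not an error in the main analysis.

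**What to change.** Under *Analysis of loss to follow-up* and in the R working list:

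1. Define loss by interval: response to the 6-month survey, and response to the 1-year survey among women who answered at 6 months.
2. Keep baseline stress as the stress variable for the first interval.
3. For the second interval, compare 6-month stress between women who did and did not answer at 1 year, by t-test or Wilcoxon test. Alternatively, fit a logistic model with group, round and 6-month stress, with group × 6-month stress as an exploratory term.
4. Take intention to leave from the same survey as the stress score in each interval, and state the timepoint of the work-family items.
5. Do not pool the intervals under a single last-observed-stress coefficient. If rows are stacked, include a survey × stress term.
6. State that a non-significant result will not be reported as absence of selective loss.

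The cost is SAP wording and a few lines of R on data already collected. There are two limits. The late-loss analysis covers only 6-month responders, and its power is low for weak dependence (about 28 to 39% at an odds ratio of 1.5 per SD).

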Building on mentorship and leadership curricula from the UW research group. Sheet Metal Workers Locals 16 and 66, and CPWR, we will design a mentorship training program to be delivered online in both synchronous (live webinars) and asynchronous (viewing previously developed or recorded materials on their own time) modalities. Journey-level workers from each intervention local will be recruited and trained to be mentors to women in their affiliated apprenticeship programs. Mentees in the intervention arm will be recruited and paired based on mutual preference with mentors within their local in two waves, allowing for at least two years of follow-up for each mentee. Women apprentices in the control locals will be recruited to participate in the evaluation only. Evaluation will assess changes in safety advocacy, selfefficacy, as well as work experience (including exposure to physical and psychosocial hazards), health (stress related indices), safety (injury experience and risk-avoidance actions) and retention in the trade. Evaluation will utilize pre- and post-program questionnaires and calculate retention rates for women apprentices in affiliated apprenticeship programs. In addition, interviews with mentors will add to a process evaluation. Using the developed curriculum and mentorship programs, and results of the evaluation, we will produce a guide to effective mentorship for women in the trades, and, in conjunction with CPWR, disseminate the materials widely. Locals participating in the program as controls will be provided with the training for any journey-level members interested in becoming mentors after the final evaluation is completed.

To help guide the development, implementation and results interpretation and dissemination, we will establish a program advisory board, who will meet annually with the research team throughout the project period. The board will include [name], Assistant to the General President of SMART, [name], Chair of the Women's Committee for SMART Local 66, [name], researcher for CPWR, a representative of the sheet metal contractors' association, TBN, an expert on mentorship for women in the trades ([name], Instructor with SMART Local 16), and a professor of construction management ([name]).

Recruitment and Assignment of Locals

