Because we have prior expectations that the mentorship program will have some degree of success, we don't want to withhold any benefits from the control locals. Thus, we will repeat the mentorship training with control locals in year five of the project. Participation will be voluntary, and no evaluation of the training will be included in this. Rather, it will be a service to the contributing local unions and their members.

Evaluation and Analysis

We have developed the following logic model of the mentorship program to describe our program and provide guidance on necessary evaluation components.

Inputs	Activities	Outputs	Short-term	Intermediate	End Outcomes
			Outcomes	Outcomes	
UW mentorship	Recruit women	Mentor-	Increase in	Reduction in	Reduced
program	apprentices	mentee interact	awareness of	perceived stress	injuries
	and mentors	on regular basis	safety & health		
Sheet Metal			risks	Increase in self-	Improved jobsite
Workers Locals	Online mentor	Mentors provide		advocacy	safety climate
16 and 66	training	emotional,	Increase in self-	behaviors	
programs		appraisal, &	efficacy		Increased
	Matching	informational		Increase in	representation of
CPWR	mentors to	support to	Improved self-	problem-	women in trade
Leadership	mentees	mentees	advocacy	solving skills	
training			knowledge		
programs	Ongoing			Increase in job	
	program		Improved social	satisfaction	
Local union	support		support at work		
engagement				Increased retention	
				in apprenticeship	
				and trade	
PLANNED WORK			RESULTS		

This logic model shows the program inputs and outputs. We will conduct both process and impact evaluations, as described below. We will measure short-term, intermediate term and long-term outcomes, however, we hypothesize that short and intermediate outcomes will be affected by our mentorship program.

Analysis plan

We will conduct a hypothesis-driven analysis of the primary outcome (perceived stress) and a limited set of secondary outcomes that we highlighted as especially important in the grant.

Research question & hypotheses

Primary research question: What is the effect of the mentorship intervention on apprentice's **perceived stress**? Hypothesis: expect a reduction in perceived stress among the intervention group (mentees) compared to controls

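### The exploratory within-arm change tests skip baseline to end-year and cannot separate mentoring from a shared trend, and the mixed model that should do so is described with and without group x time

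*Combined protocol and SAP*

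**What the plan says.** The primary hypothesis is comparative: the investigators "expect a reduction in perceived stress among the intervention group (mentees) compared to controls" (Research question & hypotheses). The Approach overview describes the design as pre-post: "Evaluation will utilize pre- and post-program questionnaires". Surveys are at baseline, 6 months and 1 year (Data).

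Three parts of the analysis plan bear on change over time:

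- **Bivariate analysis.** After the graphs and individual trajectory plots, the plan says "Stratify by group, explore change btw timepoints. Either paired t-test or single rank Wilcoxon test", and then "First compare BL to MY, then MY to EY". Outcomes are also compared between arms at each survey. The working list of steps in the Notes makes clear that those comparisons are of levels, not of differences.
- **Variables to be used in primary analysis.** Group is the exposure, followed by "Fixed effects: time, group x time". The secondary outcomes have the same list.
- **Multivariate analysis**, repeated at the end of the Notes. "To evaluate changes over time, effectiveness of the intervention will be analyzed using a mixed effects regression model". The base model described there has arm, survey and a random effect for local. No interaction is named. Covariates are kept partly by how far they move the study-arm coefficient.

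The table shells for the effect of mentorship (Tables 2 and 3) draw on mixed models only.

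**The concern.** The within-arm paired tests have three limits.

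1. They omit baseline to end-year, which is the pre-post change that the design is built around. A steady change over the year is cut into two smaller pieces.
2. Both listed tests need a mid-year survey. A woman with baseline and end-year surveys only contributes to neither.
3. Each arm is tested on its own. A change that all apprentices go through over the year looks the same as a mentoring effect. With small arms, one arm can cross 0.05 and the other not by chance alone, which invites the reading that mentees improved and controls did not.

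No bivariate step compares change between arms, so that task falls to the mixed model. There the plan gives two descriptions: one contains the term that carries the between-arm difference in change, the other does not. Neither says whether time is categorical or which coefficient answers the primary question.

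**Working it through.** The plan gives no alpha, power, effect size or SD for the outcome tests, so there is no figure of its own to reproduce. What follows is illustration.

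**Inputs from the documents (Data section).** 40 controls and 56 mentees; 18 controls and 16 mentees with all three surveys, that is 18/40 = 45%, 16/56 = 29%, and 34/96 = 35% overall.

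**Assumptions.** Paired t-test, two-sided 0.05, n = 16 and 18, no clustering by local. In steps 1 and 2, d is the mean change divided by the SD of the half-year change. Power comes from the noncentral t distribution with n - 1 degrees of freedom and noncentrality d√n.

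**Step 1: same change in both arms, no mentoring effect.** The chance that mentees are significant and controls are not, in one step, is p16 × (1 - p18).

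| d per step | p16 | p18 | Mentees only | Controls only |
|---|---|---|---|---|
| 0.25 | 0.155 | 0.170 | 0.155 × 0.830 = 0.129 | 0.144 |
| 0.35 | 0.259 | 0.289 | 0.259 × 0.711 = 0.184 | 0.214 |
| 0.50 | 0.465 | 0.516 | 0.465 × 0.484 = 0.225 | 0.276 |

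A simulation of both steps together (20,000 runs per scenario, between-survey correlation 0.5 to 0.7) used a shared full-year fall of 0.4 SD of the score. Mentees had at least one significant half-year test, and controls none, in 17-20% of trials. A between-arm comparison of the baseline-to-1-year change rejected in 4.7-5.4% of trials across all scenarios, as it should.

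**Step 2: what leaving out the full year costs.** Take a steady fall in mentees of d = 0.35 per half-year, n = 16.

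- Each half-year test: power 0.259.
- At least one of the two half-year tests significant: about 46-49% (simulation).
- Full-year test, same SD of change over 6 and 12 months: d = 0.70, power 0.745.
- Full-year test, correlation decaying with time (half-year r, full-year r²): the SD of change grows by √[(1 - r²)/(1 - r)] = √(1 + r), so d = 0.70/√(1 + r). For r = 0.5, d = 0.572 and power is 0.57. For r = 0.8, d = 0.522 and power is 0.50.

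**Step 3: what the base model without the interaction would estimate.** Suppose the effect grows linearly to E at 1 year and the data are balanced. The arm coefficient averages the arm differences at the three surveys: (0 + E/2 + E)/3 = 0.5E. Baseline, where no effect can exist, is averaged in, and the estimate is half the 1-year effect. With group x time and categorical time, the 1-year interaction term estimates E itself.

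**The case against.** A reader might infer from the bivariate section that the plan never tests the full-year change and will let the natural course of stress in apprenticeship pass for a mentoring effect. The documents do not support that. The paired tests sit among plots under the instruction "Stratify by group, explore change btw timepoints". Effectiveness is assigned to the mixed model in the next section, the variable list includes group x time over baseline to 1 year, and Tables 2 and 3 are mixed-model tables. No section bases an effect claim on a paired test. The arms are also compared at end-year, and because locals are randomized, a shared drift cancels in that comparison in expectation. All of this stands and limits the point to a minor one.

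The sizes also need care.

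- Adding both directions in step 1 gives 27%, 40% and 50% for exactly one arm significant. The larger part is controls only, which would not suggest that mentoring works.
- Setting 26% against 75% compares one half-year test with the full-year test under equal SDs. The plan runs two half-year tests, and with decaying correlation the comparison is about 46-47% for at least one of them against 50-57%.
- The paired tests are not expressly confined to women with all three surveys, so n for baseline to mid-year may exceed 16 and 18. The documents do not say how many women lack only the mid-year survey.

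The defence rests on the group x time model, though, and the base-model text leaves that term out. To that extent the safeguard is not firm.

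**Conclusion.** The point holds in a limited form. The exploratory change tests omit baseline to end-year, exclude women without a mid-year survey, and cannot separate mentoring from a shared trend. They are not the effectiveness analysis, and the plan does not present them as such. The matter that deserves action is that the controlled contrast meant to do this work is specified in one place and missing from the base model in two others, with no primary contrast named.

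Under the stated assumptions, a shared change with no mentoring effect gives significance in mentees alone in about 13-22% of trials per step. The omitted full-year test has power of about 50-75% where each half-year test has 26%. If only the model without interaction were fitted, the arm coefficient would be half the 1-year effect under linear growth and balanced data. Effect sizes, alpha, correlations and the absence of clustering are all assumed, so these figures show direction and rough size only.

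**What to change.** In the Bivariate analysis section, replace the two half-year paired tests with wording such as: *For each woman, compute change from baseline to mid-year and from baseline to end-year, using all women who have both surveys for that interval. Present mean change by arm with 95% confidence intervals and the number contributing. Within-arm results are descriptive and are not evidence of an intervention effect.*

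In the Multivariate analysis section and its repeat in the Notes, bring the base model into line with the variable list: *The base model contains arm, survey as a categorical variable, and arm x survey, with a random effect for local. The arm x survey contrast at 1 year is the basis for any statement about the intervention.* The 10% covariate rule should then refer to this contrast, because with baseline as the reference survey the arm coefficient becomes the baseline difference. Apply the same wording to the continuous secondary outcomes, and the corresponding contrast on the model's own scale to the categorical one.

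The cost is a few sentences and a few lines of R, with no new data. The Notes show that some comparisons by group have already been run, so the change should be dated and its reason recorded.
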